1.1. Collected Only On Veterans	
Patient symptom severity (positive, negative) & relapse	SANS, SAPS (Primary Veteran Outcome)
Hospitalizations & ED visits	Medical records, provider verification
Community participation	Community Participation Measure
1.2. Collected On Veterans and their Primary Family Member/Supporter	
Health services utilization	Question, Services utilization check list, CPRS, or billing data
Medication adherence (of patient)	Standardized structured interview
Social support & loneliness	MOS & Social Loneliness Scale questionnaires
Stress	Perceived Stress Scale (PSS)
Quality of life	Quality of Life interview
Knowledge of SZ/SZA	Knowledge about Schizophrenia Interview
Coping style/problem solving skills	Social Problem Solving Inventory
Sociodemographics, background, technology experience	Questionnaire
Cognitive function	RBANS
Treatment satisfaction	CSQ-8
Participant treatment exposure	Records/logs and computer server logs
Treatment: initiation, engagement, attendance, drop-out	Records/logs and computer server logs
DSW usage	Usage automatically collected by server
Commitment to DSW	Online Community Commitment Survey (OCCS)
DSW website evaluation	Web Evaluation Instrument (Appendix 8)
Participant treatment contact time	Clinician & staff logs, DSW server logs (includes video use)

Time providing each treatment	Detailed logs and CPRS progress notes
1.3. Collected Only On Primary Family Caregiver/Support Person	
Psychological distress/burden	Caregiver burden (primary family member outcome)
1.4. Collected On Therapists and Research Staff Providing the Treatments	
Therapist & staff contact time	Records/logs
Therapist & staff time to provide treatments	Records/logs
1.5. Inform Future Implementation Efforts: Collected from Clinicians and Participants	
Semi-structured interviews	Based on Getting To Outcomes implementation framework

1.1. Collected Only on Veterans with SZ/SZA

1.1.1. Symptom severity and Relapse (SANS, SAPS, BPRS). Illness symptom severity will be assessed using the Scale for the Assessment of Positive Symptoms (SAPS) (the primary patient positive symptoms outcome) and the Scale for the Assessment of Negative Symptoms (SANS) (the primary patient negative symptoms outcome). The SAPS and SANS have high internal consistency (Cronbach's $\geq 0.66-0.83$). The summary SAPS score has high inter-rater reliability (>0.90) for our trained raters, as has the SANS (>0.80), which are comparable to published inter-rater reliabilities for these scales. We will also administer the Brief Psychiatric Rating Scale (BPRS). Relapse or 'significant exacerbation' will be defined on the basis of the standard BPRS criteria.

1.1.2. Hospitalizations & Emergency Department (ED) Visits. We will measure both the number of times that a patient has an ED visit, or is hospitalized for a psychiatric reason, and the number of days for each hospitalization. We will identify this information via self-report and collect CPRS records, or if not a VA facility, the medical records from the provider via a release of information from the participant.

1.1.3. Community Participation Outcomes. The Community Participation Measure is designed to measure changes in participation in 26 community activities (e.g., shopping, going to a coffee shop, church, or movie). It has good internal consistency (Cronbach's alpha=0.9) and test-retest reliability ($r>0.7$). We have norms available from [name] (personal communication).

1.2. Collected On Both Veterans with SZ/SZA and their Family Members

1.2.1. Health Services Utilization. These will be gathered from two sources: 1) the electronic medical records of the VA and affiliated sites, and; 2) for outside providers a checklist that we have used in previous studies will collect simple counts of utilization and provider information, for which we will obtain a release of medical records from subjects and collect utilization data from each provider. Utilization will be treated as both an outcome measure and for behavioral health visits outside of the study as mediators of improvement.

1.2.2. Antipsychotic Medication Adherence. Medication adherence will be assessed using relatively standard methods that involve obtaining self-report information on medication adherence from a patient and their primary family caregiver. Patients are asked about the extent to which they took their medication as prescribed since the last interview, or at baseline, in the past 3-months, using a five point scale from "1) never missed taking my medication" to "5) I stopped taking the medication altogether." The primary family caregiver will also be asked the question about the patient. If there

is disagreement the accepted procedure is to take the lower of the two ratings as the patient's degree of adherence.

1.2.3. Social Support & Loneliness. The MOS Social Support Survey will be used to assess perceived and actual social support. It has excellent internal consistency (Cronbach's alpha from .90 to .97) and composite reliability (ranging from .93 to .97), and is relatively brief (19 items). The Revised UCLA Social Loneliness Scale will assess subjective feelings of loneliness and isolation. It has high internal consistency ($\alpha=.89\text{-.94}$), good test-retest reliability ($r=0.73$), and convergent and construct validity.

1.2.4. Perceived Stress. Perceived stress will be measured with the 14 item Perceived Stress Scale. The scale has good internal reliability ($\alpha=0.85$) and test-retest correlation ($r=0.85$).

1.2.5. Quality of Life, Functioning. The Quality of Life Interview (QOLI) contains both subjective and objective measures of quality of life including, living situation, daily activities and functioning, family-related quality of life, social relations, work, personal safety and health as well as a global rating of life satisfaction. The QOLI has been shown to have good test-retest reliability (median $r=0.72$), internal consistency (median $\geq .85$) among its subjective subscales, fair retest reliability (median $r = .65$). It is one of the most widely used measure of QOL with psychiatric populations.

1.2.6. Knowledge of SZ/SZA. The Knowledge about Schizophrenia Interview (KASI), which we used previously, will be used to assess patient and family knowledge about SZ/SZA. The KASI is widely used and has good validity and inter-rater reliability (80% to 100%).

1.2.7. Problem Solving & Coping Style. The Social Problem Solving Inventory-Revised will be used to measure coping style. It has good test-retest reliability (0.73-0.86), internal consistency (0.65-0.9), and criterion validity, and is a common measure of coping style.

1.2.8. General Background, Sociodemographic Information, and Experience with Technology. Background and sociodemographic information will be collected from patients and family using a standard instrument. We will collect information on computer experience, distance from the VA medical center and difficulties traveling to receive treatment, the average amount of weekly face-to-face contact Veteran has with family, and friends, and so forth. We will also use a relatively questionnaire that we have used in previous studies to assess experience with relevant technologies (PCs, internet, web-browsing, smart phone, etc.), and skills with these technologies (e.g., use a mouse, use a printer, make own web-page, etc.).

1.2.9. Repeatable Battery for the Assessment of Neuropsychological Status (RBANS). The RBANS is a general measure of the severity of neurocognitive impairment. It has been shown to have high convergent validity as indicated by correlation with the WAIS-III full-scale IQ ($r=0.73$), and a composite z score derived from 22 standard measures of IQ, memory, language, motor, attention, and executive function ($r=0.79$).

1.2.10. Treatment Satisfaction. The Client Satisfaction Questionnaire (CSQ-8) will be used to assess satisfaction with treatment. The CSQ-8 is used worldwide to assess client/patient satisfaction with services. It has good internal consistency (coefficient alpha 0.86 to 0.94) and concurrent validity.

1.2.11. Participant Treatment Exposure. We will log each subject's contact with treatment in each study arm. In the in-person arm this will include session attendance and any other contact with the therapists relevant to the treatment outside of the sessions. The same will be done for the DSW arm. This will also include any usage of the website, which will be logged on the server for each participant.

1.1.12. Intervention Initiation: DSW and in-person MFG. Treatment initiation will be defined as those that consent to participate in the study and then begin treatment. For both treatments two components of initiation will be tracked. First, will be participating in the Joining Sessions, then will be participation in the PSSW.

1.1.13. Intervention Engagement: DSW and in-person MFG. We will assess the number of Veterans who become engaged in the two treatments. Based on established standards for defining therapeutic treatment engagement as returning for treatment after the intake or initial session, we have previously defined initial engagement in DSW as participating in the PSSW and then using DSW to participate in an on-line group forum (e.g., logging on to the website and posting a ‘new member’ introduction) and an educational activity (e.g., reading an article). For in-person MFG intervention engagement will also be participating in the PSSW and then attending a first in-person group meeting.

1.1.14. Intervention Attendance/Commitment: DSW and in-person MFG. The number of weeks that participants attend each treatment will be assessed. For DSW this is defined as logging on to the website for at least 15 minutes in a week. For in-person MFG meetings are every other week, so each attendance covers two weeks.

1.1.15. Intervention Drop-out: DSW and in-person MFG. We will track the number of participants who drop-out of treatment in both arms. We will track those who officially drop-out of the study, and those who indicate that they no longer wish to receive treatment, though they may not drop-out of the study.

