a. Multi-Family Group (MFG). Participants assigned to the Multi-Family Group arm will receive the standard Multi-Family Group treatment provided by the VA. The treatment includes: individual participant and individual family meetings with the study clinician(s) who is providing the MFG treatment, using in-person and phone meetings; attending a multi-family group educational meeting (the Psychoeducational Survival Skills Workshop) that will be attended by the veterans and supporters who will be in a particular group, the clinicians leading the treatment, and potentially other experts who have specific content expertise and will provide brief presentations on a particular educational topic (e.g., how medications act to treat schizophrenia); and bi-weekly meetings of the group that will be led by the two clinicians. The study clinicians will be supervised by the study Investigators.

The MFG model begins with two participant engagement activities. The first activity is joining sessions where the therapist meets with each individual participant (veteran, and when present supporter), to develop a collaborative relationship and discuss MFG. These meetings can involve both individual participant meetings as well as joint family meetings (i.e., veteran and his/her supporters). The number of meetings varies by individual and family need (as jointly determined by the therapist and the participants). Following these meetings with the participants who will form an individual in-person group, a Psychoeducational Survival Skills Workshop (PSSW) is held. The PSSW varies in length from 2 to 7 hours, depending on the educational needs of the participants and the amount of time they are able to tolerate a meeting. The PSSW includes educational presentations on schizophrenia, and group discussions. The specific educational topics are chosen and adapted based on the needs of the participants as determined by the therapists during the joining sessions. Once the PSSW is held the multi-family treatment sessions begin on a bi-weekly basis. Each meeting is structured around reviewing the results of a previous meeting's effort to solve a member's problem and then identifying one new problem of a group member to be solved via the group problem solving process.

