b. Daily Support Website (DSW). Participants assigned to be in the Daily Support Website arm will receive access to this website and its associated functionalities. The DSW provides the following five resources. (1) Three on-line group forums. One for persons with SZ/SZA only (the SZ/SZA peer group), one for family/supporters only, and a combined group for both persons with SZ/SZA and support persons. In each group the therapists emphasized discussions that focus on problem-solving, alleviating stresses, and encouraging peer interactions. (2) Educational materials and tutorials. (3) A section to ask questions and receive an answer from the therapists associated with the project. (4) A library of previously asked and answered questions. (5) A list of community resources. Those who do not have a computer will have a computer (e.g., laptop, touch pad, or chrome book) provided to them, and Internet service, both free of charge to allow them to participate in the intervention. After their participation is over they will return the equipment.

The DSW treatment begins with two participant engagement activities. The first activity is joining sessions where the study therapist(s) meets with each individual participant (veteran, and when present supporter). These meetings can be in-person, via phone or over the internet. The purposes of the meetings are to develop a collaborative relationship, discuss the DSW, facilitate comfort with the e-health approach to receiving treatment, and develop an individual goal or identify a current 'issue' or 'complaint' that is bothering the individual. These meetings can involve both individual participant meetings as well as joint family meetings (i.e., veteran and his/her family/supporters). The number of meetings varies by

individual and family need (as jointly determined by the therapist and the participants). During the initial treatment period a therapist or research staff member may call a participant to ensure there are no issues with accessing the DSW, such as problems with equipment or lack of understanding of one or more aspects of using the DSW.

2. Participant Data collection. Outcomes data will be collected at scheduled time points of baseline (0), 6, 12, and 15 months. Each of these sessions is estimated to take about 2 hours. The data to be collected is described in Table 4.1.

Table 1.1. Data collection

Information	Measure

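### DSW engagement depends on a workshop (PSSW) that the DSW arm description never mentions, and it has one more component than MFG engagement, yet Hypothesis 1.3 compares the arms on it

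*Combined protocol and SAP*

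**What the plan says.** Four places in the combined protocol and SAP bear on this.

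- **Section 1.0, item 1.a (MFG)** gives two engagement activities and describes both. Joining sessions come first, and then: "Following these meetings with the participants who will form an individual in-person group, a Psychoeducational Survival Skills Workshop (PSSW) is held".
- **Section 1.0, item 1.b (DSW)** opens in the same way: "The DSW treatment begins with two participant engagement activities. The first activity is joining sessions where the study therapist(s) meets with each individual participant". No second activity follows. The text moves on to calls that check access to the website.
- **Section 1.1.12 (initiation)** states: "Treatment initiation will be defined as those that consent to participate in the study and then begin treatment". It adds: "For both treatments two components of initiation will be tracked". These are listed as follows: "First, will be participating in the Joining Sessions, then will be participation in the PSSW".
- **Section 1.1.13 (engagement)** describes "initial engagement in DSW as participating in the PSSW and then using DSW to participate in an on-line group forum", and adds an educational activity such as reading an article. For the other arm: "For in-person MFG intervention engagement will also be participating in the PSSW and then attending a first in-person group meeting".

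Hypothesis 1.3 (section 1.7.1) then predicts that DSW will show higher initiation and engagement than in-person MFG.

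**The concern.** An analyst given this document could not code DSW engagement. The first condition is attendance at a workshop whose existence, format and timing in that arm are not stated. Separately, the DSW definition asks for an educational activity that has no counterpart in the MFG definition, although section 1.1.13 derives both from one general standard, that of coming back after the first session.

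What is at stake is Hypothesis 1.3. If the rule is left open, it will have to be settled when attendance and server logs are already visible, and the choice could then decide the result. SAPS, SANS, caregiver burden and the sample size do not depend on these definitions.

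**Working it through.** The plan gives no figure for initiation or engagement, so there is none to reproduce. The check is a comparison of the text, followed by a short test of whether a size or direction can be derived.

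**Step 1. Arm descriptions against definitions.**

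| Item | MFG | DSW |
|---|---|---|
| Engagement activities announced (1.0) | 2 | 2 |
| Engagement activities described (1.0) | 2 (joining sessions, PSSW) | 1 (joining sessions) |
| Tracked components of initiation (1.1.12) | joining sessions, PSSW | joining sessions, PSSW |
| Components of engagement (1.1.13) | 2 (PSSW, first group meeting) | 3 (PSSW, forum, educational activity) |

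Two separate problems follow. The PSSW appears in the DSW definitions but not in the DSW description. The educational activity is an extra DSW component, and it would remain even if a DSW workshop were described.

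**Step 2. What the extra component does within DSW.** For any events A (PSSW and forum) and B (educational activity), P(A and B) ≤ P(A). The third component therefore cannot raise the DSW engagement rate and may lower it. The amount could be close to zero if nearly everyone who posts also reads.

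**Step 3. Whether a between-arm size or direction follows.** Suppose a PSSW is held in both arms. The step rates below are assumptions; none is in the documents.

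- Equal, independent steps with pass rate q, so DSW = q³ and MFG = q². At q = 0.7: 0.343 v 0.490, DSW about 15 points lower. At q = 0.8: 0.512 v 0.640, about 13 points lower. At q = 0.9: 0.729 v 0.810, about 8 points lower.
- Unequal steps: PSSW 0.80 in both arms, first MFG meeting 0.67, DSW forum and article together 0.90. MFG = 0.80 × 0.67 = 0.536 and DSW = 0.80 × 0.90 = 0.720, so DSW is about 18 points higher.

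The sign changes with the assumed rates, so neither size nor direction can be claimed.

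**Step 4. Counts or proportions.** Section 1.1.13 speaks of the number of Veterans who engage. Section 1.8 plans to enrol 70 in MFG and 47 in DSW. At an identical engagement proportion, the MFG count would be 70/47 = 1.49 times the DSW count. Only proportions of those randomised are comparable.

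**The case against.** The strongest reply is that this is a drafting gap. Item 1.b uses the same opening as item 1.a, where the second activity is the PSSW, and sections 1.1.12 and 1.1.13 both assume a PSSW in the DSW arm. Read together, they suggest that a DSW workshop was intended and left undescribed. The silence elsewhere is weak evidence of absence: the five listed DSW resources are what the website provides, and joining sessions are not among them either; the opening paragraph of section 1.0 omits the PSSW for MFG too. This stands. A reader might infer that no DSW participant can meet the engagement definition, so that the rate is 0 of 47. The documents do not support that, because it holds only if no PSSW is delivered in that arm.

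A reader might also infer that initiation requires the PSSW, or is harder to reach in DSW. That is not supported either. Initiation is defined as consenting and then beginning treatment; the two components are tracked, and they are the same in both arms. What remains is that the plan does not say which component counts.

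Third, three components against two need not be the harder test. Posting and reading could happen in one log-on, whereas the MFG step is attendance in person, and travel difficulty is a stratification factor. The plan's expected non-completion, up to 33% in MFG and up to 10% in DSW, is not a step rate, but it makes equal step rates doubtful. This stands, and it is why no deficit is claimed.

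Finally, a stricter DSW criterion would work against Hypothesis 1.3 and would not favour a false positive. That is fair, but it does not answer the problem: a real difference could be missed, and an unsettled rule can be resolved later in either direction.

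**Conclusion.** The point holds as an inconsistency and an inequality of definition. The DSW engagement criterion includes an event not described for that arm, and it has three components against two for MFG, with no justification given for the difference. The initiation measure does not say which tracked component counts. Hypothesis 1.3 compares the arms on both measures, so it cannot be analysed unambiguously as written.

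The effect on the comparison has no derivable size or net direction. The only result free of assumptions is that the added educational component cannot raise the DSW rate. The conclusion rests on the text alone and holds whether or not a DSW workshop is held: without one, the definition and the arm description conflict; with one, the description is incomplete and the extra component remains. The primary outcomes, sample size and power are unaffected. The change should be made before the data for Hypothesis 1.3 are examined.

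**What to change.** 1. Reconcile section 1.0 (item 1.b) with sections 1.1.12 and 1.1.13 on whether the DSW arm has a PSSW and, if so, describe it. Which version is right is for the sponsor to state.
2. For Hypothesis 1.3, name the component that counts as initiation, the same in both arms; for example, at least one joining session.
3. Define engagement by matching steps: the first MFG group meeting attended, against the first participation in a DSW group forum. Require the PSSW in both arms or in neither. Matching forum to meeting avoids a looser rule for DSW alone, as would arise if either a forum or an educational activity were enough.
4. Report the DSW educational activity and PSSW attendance separately.
5. Analyse initiation and engagement as proportions of all participants randomised to each arm.

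The cost is wording. Attendance records, therapist contact logs and DSW server logs are already planned and should supply each step. The small downside is less comparability with the team's earlier DSW definition, which can be reported as a secondary measure.

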1.3. Collected Only On Primary Family Caregiver/Support Person

1.3.1. Family member psychological burden: Caregiver Burden Scale. We will measure psychological burden using an instrument we have experience with that was specifically developed for family members of those with SMI. The global score has good reliability ($\alpha=0.85$), and the 6-subscales have good construct validity and reliability (the average alpha reliability score is 0.82).

1.4. Collected Only on DSW Users

1.4.1. DSW website Usage. The programming of the DSW application will automatically identify each user who enters DSW and track every page used, the amount of time spent on each page, any video interactions a user is involved with, and the time of day. It will also identify whether access was via mobile phone or personal computer. By the use of cookies we will determine whether access was from a subject’s registered home computer or another computer. These data will allow us to describe subjects’ complete usage patterns, and will allow us to break the usage down by each content or page of DSW.

1.4.2. DSW Commitment: Online Community Commitment Survey (OCCS). This 15-item survey measures three distinct forms of on-line commitment (using 7-point Likert scales ranging from “strongly disagree” to “strongly agree”): continuance (e.g., “the content of this site is too valuable for me to stop using”); normative (“this site deserves my loyalty”); and affective (“I feel like a part of the group at this site”). These commitment constructs and scales have been used in prior studies of user behavior in online groups.

1.4.3. Website Evaluation Instrument (WEI). Subjects’ satisfaction with, and reactions to, DSW will be assessed using the WEI. Our research team developed and has used the instrument in our prior web studies. It was developed from several standard instruments, and measures helpfulness, understandability, value, ease of use, users’ preferences for each of the on-line modules versus obtaining each service using traditional in-person methods, problems, suggested changes, and so forth.

